7.8 Long term follow-up assessments

There will be no long term follow-up assessments.

7.9 Withdrawal procedures

Should participants wish to withdraw during the actual study visit the trial process will depend on what stage of the study is reached. If the drug has not yet been administered, then the participant can withdraw immediately and replaced with another eligible candidate. If melatonin or placebo has been given then no further drug will be given and no more samples will be obtained. Data and samples obtained with consent will be retained. If the participant withdraws the reasons, if given, will be recorded. If the target of 25 completers (ie both arms) is not reached after 32 randomised subjects we will continue to recruit if time allows.

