Internal ref. no. (or short title)	MIDNIGHT Trial				
Clinical Phase	Phase 2				
Trial Design	Randomised, double blind, pla	acebo controlled, cross over			
Trial Participants	Intensive care unit medical ar	nd nursing staff			
Planned Sample Size	32				
Treatment duration	3 nights x 2 occasions				
Follow up duration	End of final study visit				
Planned Trial Period	3 years				
	Objectives Outcome Measures				
Primary	To determine the feasibility of a trial of Circadin vs placebo in medical and nursing staff working nightshifts on the intensive care unit.	Recruitment and randomisation of 25 individuals completing both arms of the crossover design.			
Secondary	Determine effect of night shift working on transcriptome.	Differential gene expression between baseline and end of shift on Day 1, and end of shifts series on Day 4.			
	Determine effect of Circadin on transcriptome.	Differential gene expression between placebo and active arms on Day 4.			
	Determine effect of night shift working on cytokine profile.	Serum IL-6 and TNF α levels at baseline, end of shift on Day 1 and on Day 4.			
	Determine effect of Circadin on cytokine profile	Serum IL-6 and TNF α levels after placebo and active arms on Day 4.			
	Determine metabolism of Circadin	Serum melatonin and 6- hydroxymelatonin sulphate levels at each time point			
	Determine effect of Circadin on sleep measures	Verran and Snyder-Halpern sleep scale, Epworth sleepiness scale, data from wristband activity monitor			

	Determine effect of Circadin on psychomotor function Determine whether usual sleep habits impact on effect of Circadin	Psychomotor vigilance task, double digit addition test. Usual sleep habits and owl- lark questionnaires.		
	trial.	focus group.		
Intervention	Circadin [™] or matching placebo			
Formulation, Dose, Route of Administration	Oral, 6mg, modified release tablets			

FUNDING AND SUPPORT IN KIND

FUNDER(S) (Names and contact details of ALL organisations providing funding and/or support in kind for this trial)	FINANCIAL AND NON FINANCIAL SUPPORT GIVEN
British Journal of Anaesthesia/Royal College of Anaesthetists	Financial support for the study.
Flynn Pharma	Provision of Circadin and matching placebo, free of charge.

ROLE OF STUDY SPONSOR AND FUNDER

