3.3 Primary endpoint/outcome

The primary endpoint is successful completion of the trial, defined as recruitment, randomisation and protocol completion of 25 individuals ie both arms of the crossover design. We aim to recruit 32 subjects to account for dropout and non-completion.

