3.5 Secondary endpoints/outcomes

Objectives	Outcome Measures	Timepoint(s) of evaluation of this outcome measure (if applicable)				
Primary Objective	Randomisation of 32 subjects with the aim of 25 completing both arms of the crossover design. This will allow for at least 20% attrition rate which is fairly standard in such studies.					
Secondary Objectives	Determination of drop out, non completion and retention rate	Trial end.				
	Differential gene expression	and end of shifts series on Day 4.				
	Differential gene expression between placebo and active arms.	Blood samples Day 4 after each shift series.				
	Serum IL-6 and TNF α levels.	Blood samples on Day 1, and end of shifts series on Day 4 .				
	Serum IL-6 and TNF α levels after placebo and active arms.	Blood samples Day 4 after each shift series.				
	Serum melatonin and 6- hydroxymelatonin sulphate levels at each time point	Blood samples on Day 1 before shift, and end of each shift for shift series.				
	Verran and Snyder-Halpern sleep scale, Epworth sleepiness scale, data from wristhand activity monitor	VSH before each shift. ESS before, during and after each shift. Activity monitoring during each sleep period.				
	Psychomotor vigilance task, double digit addition test	PVT and DDAT before and after each shift				
	Usual sleep habits and owl-lark questionnaires.	Before randomisation.				
	Questionnaire about trial.	Trial end.				
	Focus group on trial.	Trial end (requires additional consent)				

*Additional consent will be obtained

Figure 1

Summary of the trial design.

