10 STATISTICS AND DATA ANALYSIS

10.1 Sample size calculation

The number of volunteers in this pilot study is a pragmatic number and has been selected based on this being a suitable and sufficient number for a pilot study to enable determination of trial feasibility, including acceptance of the trial design by participants, and drop out rates/retention. In addition we have considered funding issues and previous studies of a similar design [8,34-36]. However, the number chosen and the cross over design will maximise the opportunity for finding any effect. We aim to recruit 32 subjects to cover losses due to drop outs and with the aim of obtaining 25 subjects who complete the protocol. This will allow an initial exploration of potential effects to enable a formal sample size to be calculated for a definitive subsequent trial. We propose that should any subject withdraw or fail to complete both arms of the trial, replacement participants will be sought if this were prior to any treament allocation. Subjects will be randomised in blocks of 8 such that of each 8 participants recruited, four will receive melatonin first and four will receive plaecbo first. The investigators and the subjects will not know the allocation; only pharmacy will know. This scheme will ensure the allocation is evenly spread over the study duration to account for any effects of seasonality.

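### Reaching 25 completers is weak evidence of acceptable retention, because the number randomised may grow past 32 with no maximum and no completion proportion is required

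*Protocol*

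**What the plan says.** Protocol section 3.3 gives the endpoint as a number of people: "The primary endpoint is successful completion of the trial, defined as recruitment, randomisation and protocol completion of 25 individuals ie both arms of the crossover". The synopsis agrees. The primary-objective row of the table in 3.5 gives the plan behind it: "Randomisation of 32 subjects with the aim of 25 completing both arms of the crossover design", followed by "This will allow for at least 20% attrition rate which is fairly standard in such studies".

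Section 7.9 then opens the denominator: "If the target of 25 completers (ie both arms) is not reached after 32 randomised subjects we will continue to recruit if time allows". The synopsis sets the whole trial at three years, and 10.2 gives a recruitment ceiling of two volunteers a week. Neither is turned into a maximum number randomised or a closing date for recruitment.

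Replacement is described twice. Section 7.9 says: "If the drug has not yet been administered, then the participant can withdraw immediately and replaced with another eligible candidate". Section 10.1 says that "replacement participants will be sought if this were prior to any treament allocation".

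Retention is not ignored. Section 10.1 gives drop-out and retention among the reasons for choosing the number of volunteers, 3.5 lists them as a secondary outcome, and 10.3.2 (primary outcome analysis) describes recruits, drop-outs and completers. None of these places sets a level that would count as acceptable.

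**The concern.** A pilot of this kind has to tell the designers of a definitive trial what fraction of randomised staff will complete both series of night shifts. A count of 25 answers that only if the number randomised is fixed. At 32 the count carries a definite meaning, about 78% completion. Once recruitment may go on, the same count is compatible with much lower completion, and the protocol would still call its primary endpoint met.

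The two replacement cut-offs add to this. Someone who is randomised but withdraws before the first dose is replaceable under 7.9 and not under 10.1. Whether that person stays in the denominator is therefore not settled where the endpoint is defined.

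**Working it through.** **Inputs.** Target 25 completers (3.3); planned number randomised 32 and attrition allowance of at least 20% (3.5); extension rule without a maximum (7.9); recruitment of up to 2 a week (10.2); trial period 3 years (synopsis). Completion rates, totals above 32 and recruitment rates below 2 a week are not in the protocol. They are assumed here and shown as ranges.

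**1. The plan's own figure.** 25 / (1 − 0.20) = 31.25, rounded up to 32. This reproduces the planned number. The allowance is 32 − 25 = 7 losses, and 7/32 = 21.9%.

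**2. What 25 completers can mean.** Exact (Clopper-Pearson) 95% intervals for x = 25 of n run from the 2.5% point of Beta(x, n − x + 1) to the 97.5% point of Beta(x + 1, n − x).

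| Randomised | Completion | Exact 95% CI |
|---|---|---|
| 32 | 78.1% | 60.0% to 90.7% |
| 40 (assumed) | 62.5% | 45.8% to 77.3% |
| 50 (assumed) | 50.0% | 35.5% to 64.5% |

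All three rows meet the endpoint as worded.

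**3. Chance of meeting the endpoint.** With n randomised and independent completion at true rate p, the chance is P(X ≥ 25) for X ~ Binomial(n, p).

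| True completion | n = 32 | n = 40 (assumed) | n = 48 (assumed) | n = 64 (assumed) |
|---|---|---|---|---|
| 85% | 0.904 | >0.999 | >0.999 | >0.999 |
| 80% | 0.698 | 0.997 | >0.999 | >0.999 |
| 70% | 0.212 | 0.885 | 0.997 | >0.999 |
| 60% | 0.025 | 0.440 | 0.897 | >0.999 |
| 50% | 0.001 | 0.077 | 0.443 | 0.970 |

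At 60% completion and n = 50 the chance is 0.943. With 32 fixed, the criterion separates good from poor retention. With extension that separation weakens quickly. The expected number randomised to reach 25 is 25/p: 31.3 at 80%, 41.7 at 60% and 50.0 at 50%.

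**4. Does time limit the extension?** The share of the three years available for recruitment is not stated, so 104 and 156 weeks are taken as an assumed range.

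| Recruits per week | Weeks to 32 | Recruits in 104 to 156 weeks |
|---|---|---|
| 2 (stated ceiling) | 16 | 208 to 312 |
| 0.5 (assumed) | 64 | 52 to 78 |
| 0.25 (assumed) | 128 | 26 to 39 |

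Near the ceiling, time hardly binds. At 0.25 a week it does, and the target can be missed.

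**5. Replacement.** Under 10.1 a replaced person was never allocated and so is outside the randomised denominator. Under 7.9 a replaced person may already have been randomised. If, say, 3 such people were replaced and left out of the count, 25 of 35 randomised (71.4%) would be presented as 25 of 32 (78.1%).

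**The case against.** The best defence is that this is a pilot with no formal sample size and a descriptive primary analysis. Section 10.3.2 reports drop-outs and completers, 10.2 promises a CONSORT diagram, and 10.7 defines an all-randomised population whether or not people were dosed or completed. A result of 25 of 50 would be visible to any reader, and completion among the first 32 could be worked out from data already collected. Continuing past 32 also serves a stated aim, since 25 completers are wanted to explore effects and to size a later trial. All of this stands. It means that a criterion is missing, not the information.

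Four stronger readings are tempting and are not supported:

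- A reader might infer that the endpoint can never show infeasibility. The extension is conditional on time within a three-year trial, and slow recruitment, itself part of the endpoint, could leave the count short.
- A reader might infer that withdrawals in general are replaced. Both sections limit replacement to people not yet dosed or not yet allocated.
- A reader might infer that retention is only a secondary matter. Drop-outs and completers are part of the primary outcome analysis; they simply carry no threshold.
- A reader might take the allowance of at least 20% as stated the wrong way round. An allowance of 21.9% is at least 20%, and 32 follows from 25/0.80.

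There is also a fair objection to the remedy: 25 of 32 as a hard threshold fails about 30% of the time when attrition is exactly 20%, the figure used for planning.

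**Conclusion.** The point holds as a weakness in the definition of the primary endpoint. A count of 25 with an open denominator is weak evidence of acceptable retention, because it can be met at 78%, 63% or 50% completion. At a true completion rate of 60%, the chance of meeting it rises from 2.5% with 32 randomised to 44% with 40 and 94% with 50.

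These figures assume independent completion at a common rate, and totals that the protocol neither states nor excludes. How far the extension would really go depends on the recruitment rate, for which only a ceiling is given. The replacement cut-offs in 7.9 and 10.1 do differ on the text, whatever is assumed. Since completion data will be collected and described in any case, the change is well worth making, but the trial does not stand or fall by it.

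**What to change.** In 3.3 and 7.9, base the feasibility conclusion on the proportion completing both series among the first 32 randomised, with its exact 95% confidence interval. Count every randomised person in that denominator, including anyone who is replaced. Keep the option to recruit further, but report people after number 32 separately, as contributing to the exploratory analyses. Reconcile the replacement cut-offs in 7.9 and 10.1 so that it is clear who counts in the 32.

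An alternative is to state a maximum number randomised, a recruitment window and a minimum completion proportion, and to report any extension separately.

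The edit is to wording only and keeps the protocol's own numbers. The cost lies in how the criterion behaves. If 25 of the first 32 is used as a strict pass mark, it is met only 70% of the time at a true 20% attrition, and 90% of the time at 15%. The protocol should state this if it adopts a strict threshold. Reporting the proportion and its interval without a hard pass mark avoids that cost.

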7.10 Storage and analysis of samples

Blood samples (20ml) will be obtained by venepuncture by a appropriately trained person. Samples will be placed into appropriate blood collection tubes. Samples will be transported within 2h under containment level 2 rules (SOP-IMS-006) in the Institute of Medical Sciences (IMS) for preparation of serum or RNA and storage according to a standard operating procedure (SOP-IMS-005). Samples will be labelled with a unique anonymised ID number only. Serum and RNA samples will be stored immediately at -70 (+/- 10) degrees C in a designated ultra low temperature freezer with daily temperature monitoring (SOP-IMS-001). All samples will be analysed locally.

We recognise that it is the responsibility of the trial site to ensure that samples are appropriately labelled in accordance with the trial procedures to comply with the 1998 Data Protection Act. Biological samples collected from participants as part of this trial will be transported, stored, accessed and processed in accordance with national legislation relating to the use and storage of human tissue for research purposes and such activities shall at least meet the requirements as set out in the 2004 Human Tissue Act and the 2006 Human Tissue (Scotland) Act.

7.12 End of trial

The end of the trial is defined as 6 months after the last volunteer has received both study treatment arms – this is to allow final sample handling and data analysis and conduct and analysis of focus groups.

8 TRIAL MEDICATION

Melatonin will be administered as Circadin (6mg as 2mg tablets, Flynn Pharmaceuticals Ltd.) which has EMA regulatory approval and is a slow release formulation with a blood concentration profile resembling that of endogenous melatonin. Placebo tablets will also be manufactured for us by Flynn. Both the melatonin and placebo will be provided free of charge and will be dispensed by the Clinical Trials Pharmacy who will also be responsible for drug accountability. Commercial stocks of Circadin will be delivered, with a self-life of 2.5-3 years under normal pharmacy conditions. The bulk placebo will have nominally a 3 year shelf-life and the bulk product will be stored in pharmacy in conditions to protect it from light, moisture and excessive temperature. HDPE bottles will be used for post-randomisation dispensing of both active drug and placebo. Drug accountability will be delegated to the Clinical Trials Pharmacist, [name].

8.1 Name and description of the interventional product

The product is Melatonin (Circadin[™]) and an identical placebo tablet both provided by Flynn Pharma Ltd.

8.2 Legal status of the drug

Melatonin is currently licenced for use in the UK but the study has been classified by the MHRA as **not** being a CTIMP and therefore does **not** require a Clinical Trial Authorisation (CTA). The drug will however only to be used by the named investigators, for the volunteers specified in this protocol, and within this trial only.

8.3 Summary of Product Characteristics (SmPC)

Please see the Investigator Brochure (IB) and the Summary of Product Characteristics (SmPC), available at https://www.medicines.org.uk/emc/medicine/25643.

Flynn Pharma has committed to inform the Chief Investigator should there be any updates to the SmPC.

8.4 Drug storage and supply

Drug (active and placebo) storage will be at <25°C. See SmPC for details. The shelf life is 3 years.

Melatonin and identical placebo tablets have been supplied by the manufacturer (Flynn Pharmaceuticals Ltd) and will be stored in the Aberdeen Royal Infirmary Clinical Trials Pharmacy. A prescription sheet will be sent to pharmacy indicating the trial number, unique identifier and subject name. Pharmacy will dispense active or placebo drug depending on a randomisation list previously provided. Labelling will be according to Annex 13 of Volume 4 of The Rule Governing Medicinal Products in the EU: Good Manufacturing Practices".

Empty bottles and unused medication will be returned to Pharmacy who will maintain drug accountability records.

8.5 Preparation and labelling

Flynn Pharma have supplied the Circadin and matching placebo tablets (2mg) as a single bulk supply from a single batch for dispensing by the Clinical Trials Pharmacy. Commercial stocks of Circadin are provided. Both active and placebo drug will have a shelf-life of 3 years. Drug accountability will be delegated to the Clinical Trials Pharmacist, [name].

Table 1	Study Overview	(applies to both shift series))
---------	----------------	--------------------------------	---

Shift	Blood sample	Sleep habits/CSM questionnaire	PVT/DDAT	Trial drug	VSH sleep scale	ESS	Post trial questionnaire	Focus group*
First shift before shift during shift end of shift before sleeping	4 4 4	~	* *	~	~	4 4 4		
Second shift before shift during shift end of shift before sleeping	~		✓ ✓	~	✓	*		
Third shift before shift during shift end of shift before sleeping	~		* *	~	✓	* * *		
Fourth shift before shift	11		V		4	*		
After all visits							1	✓

 \checkmark = Blood sample for gene array \checkmark = Blood sample for melatonin/cytokines \checkmark = Blood sample for pathology CSM = composite scale of morningness PVT/DDAT = psychomotor vigilance task/double digit addition test VSH = Verran and Snyder-Halpern sleep scale ESS = Epworth sleepiness scale * requires additional consent

8.6 Dosage schedules

Subjects will receive an oral dose of 6mg Circadin or a placebo of identical appearance (as $3 \times 2mg$ tablets) just before bedtime, on three consecutive nights, on two occasions. One of those occasions the subjects will receive the active Circadin and on the other they will receive the placebo. The order will be randomised. Subjects will be asked to take the medication 1-2 hr before planned bedtime/sleeping time with a small snack. The time of dosing, the time of bedtime and the type of snack will be recorded.

8.7 Dosage modifications

There will be no dosage modifications allowed.

8.8 Known drug reactions and interaction with other therapies

Treatment will be stopped if a patient develops an unexpected reaction thought to be due to Circadin administration. This might include, but is not limited to, vomiting, diarrhoea or suspected anaphylaxis. Fluvoxamine or nifedipine interfere with the metabolism of melatonin but are not considered to be harmful. Subjects taking these drugs would not be eligible for the study and participants would be withdrawn should they require these drugs for medical reasons during the study.

8.9 Concomitant medication

Participants receiving chronic medication other than oral contraceptives will not be recruited. If subjects require medication during the trial this will be allowed, apart from fluvoxamine, nifedipine, sedatives or other drugs likely to cause drowsiness, but will be recorded.

8.10 Trial restrictions

Apart from specified medications, avoidance of sunlight during the return home after the night shifts and not consuming alcohol there are no trial restrictions.

8.11 Assessment of compliance

Subjects will be take their trial drug at home and asked to return the empty container. They will be asked to confirm the time that they took the trial drug. Non-compliance will be recorded.

9 PHARMACOVIGILANCE

9.1 Definitions

Term	Definition
Adverse Event (AE)	Any untoward medical occurrence in a participant to whom a medicinal product has been administered, including occurrences which are not necessarily caused by or related to that product.
Adverse Reaction (AR)	An untoward and unintended response in a participant to an investigational medicinal product which is related to any dose administered to that participant.
	The phrase "response to an investigational medicinal product" means that a causal relationship between a trial medication and an AE is at least a reasonable possibility, i.e. the relationship cannot be ruled out.
	All cases judged by either the reporting medically qualified professional or the Sponsor as having a reasonable suspected causal relationship to the trial medication qualify as adverse reactions.
Serious Adverse	A serious adverse event is any untoward medical occurrence that:
Event (SAE)	 results in death is life-threatening requires inpatient hospitalisation or prolongation of existing hospitalisation results in persistent or significant disability/incapacity consists of a congenital anomaly or birth defect
	Other 'important medical events' may also be considered serious if they jeopardise the participant or require an intervention to prevent one of the above consequences.
	NOTE: The term "life-threatening" in the definition of "serious" refers to an event in which the participant was at risk of death at the time of the event; it does not refer to an event which hypothetically might have caused death if it were more severe.
Serious Adverse Reaction (SAR)	An adverse event that is both serious and, in the opinion of the reporting Investigator, believed with reasonable probability to be due to one of the trial treatments, based on the information provided.
Suspected Unexpected Serious Adverse Reaction	A serious adverse reaction, the nature and severity of which is not consistent with the information about the medicinal product in question set out:
(SUSAR)	 in the case of a product with a marketing authorisation, in the summary of product characteristics (SmPC) for that product in the case of any other investigational medicinal product, in the investigator's brochure (IB) relating to the trial in question

